### **Substudy 1:**

The first 11 visit windows for data between scheduled assessments in this study are:

- Day 2, visit window 2-4
  - Day 8, visit window 5-11
  - Day 15, visit window 12-18
  - Day 22, visit window 19-25
  - Day 29, visit window 26-32
  - Day 36, visit window 33-39
  - Day 43, visit window 40-52
  - Day 64, visit window 53-73
  - Day 85, visit window 74-94
  - Day 106, visit window 95-115
  - Day 127, visit window 115-136
- Visit windowing are done separately for each assessment based on the schedule of events specific to that assessment
  - Should visit date be missing (due to partial or missing dates), then visits are assigned to the nominal visit at which that assessment was recorded, and no windowing is performed.
  - For visit-based summaries, if there is more than one value per participant within a time window then the closest value to the scheduled visit date is summarised, or the earlier, in the event the values are equidistant from the nominal visit date. In the scenario that a complete visit date falls into the same visit as one that has been assigned due to missing data, the visit with the complete date is summarised. The listings highlight the value for the participant that contributed to the summary table, wherever feasible. Note: in summaries of extreme values, all post baseline values collected are used including those collected at unscheduled visits regardless of whether the value is closest to the scheduled visit date.
  - For summaries at a participant level, all values are included, regardless of whether they appear in a corresponding visit-based summary, when deriving a participant level statistic such as a maximum.

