### 3.3.2 Visit Window

For safety, time windows are defined for any presentations that summarize values by visit. The following conventions apply:

- The time windows are exhaustive so that data recorded at any timepoint has the potential to be summarised. Inclusion within the time window is based on the actual date and not the intended date of the visit.
- All unscheduled visit data have the potential to be included in the summaries.

- The window for the visits' following baseline is constructed in such a way that the upper limit of the interval falls halfway between the two visits (the lower limit of the first post-baseline visit is Day 2). If an even number of days exists between two consecutive visits, then the upper limit is taken as the midpoint value minus 1 day.

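### SAP 3.3.2 places Day 115 in two safety visit windows, and its window list cannot be reconciled with its own midpoint rule

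*SAP*

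**What the plan says.** SAP 3.3.2 (Visit Window) sets the windows for safety summaries by visit. They are meant to leave no day uncovered: "The time windows are exhaustive so that data recorded at any timepoint has the potential to be summarised". Assignment uses the actual date. Each window is "constructed in such a way that the upper limit of the interval falls halfway between the two visits", the first post-baseline window starts on Day 2, and there is an adjustment: "If an even number of days exists between two consecutive visits, then the upper limit is taken as the midpoint value minus 1 day".

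The Substudy 1 list then gives eleven windows. It opens with "Day 2, visit window 2-4" and "Day 8, visit window 5-11" and continues 12-18, 19-25, 26-32, 33-39, 40-52, 53-73 and 74-94 for Days 15, 22, 29, 36, 43, 64 and 85. The last two are "Day 106, visit window 95-115" and "Day 127, visit window 115-136".

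The same section says that windowing is done separately for each assessment on its own schedule. When one window holds several values, the one closest to the scheduled day is summarised, or the earlier if two are equidistant. Extremes and participant-level statistics use all values.

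**The concern.** The overlap needs no interpretation: Day 115 closes one window and opens the next. The closest-value rule chooses among values inside one window, so it does not say which window a Day 115 value enters. Two programmers could resolve this differently, or the same value could be summarised at both visits.

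The second problem is that the change from 7-day to 21-day spacing alters how the limits are rounded, although the rule gives no reason for it. Where the limits stop short of halfway, a value is credited to the more distant visit.

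At stake are the by-visit summaries of laboratory values and vital signs, which support the primary safety endpoints. Boundary days can occur. The SAP counts study day from first treatment, whereas the footnote to protocol Table 13 times safety visits from the most recent dose, and protocol 10.6.6 allows dosing to be held. Unscheduled values are also eligible for the summaries.

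**Working it through.** **Inputs.** The visit days and listed windows come from the Substudy 1 list in SAP 3.3.2, and the rule from the same section. The visit after Day 127 is taken as Day 148, because protocol Table 13 continues every 3 weeks (127 + 21 = 148).

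**Reading 1: the even-number test refers to the gap length.** For consecutive visits a and b, the midpoint is m = (a + b)/2. If b − a is even, the upper limit is m − 1. If it is odd, m falls on a half day and the upper limit is the last whole day before it. Each lower limit is the previous upper limit plus 1, starting at Day 2.

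| Visit | Next | Gap | Midpoint | Window by rule | Listed |
|---|---|---|---|---|---|
| 2 | 8 | 6 (even) | 5 | 2-4 | 2-4 |
| 8 | 15 | 7 | 11.5 | 5-11 | 5-11 |
| 15 | 22 | 7 | 18.5 | 12-18 | 12-18 |
| 22 | 29 | 7 | 25.5 | 19-25 | 19-25 |
| 29 | 36 | 7 | 32.5 | 26-32 | 26-32 |
| 36 | 43 | 7 | 39.5 | 33-39 | 33-39 |
| 43 | 64 | 21 | 53.5 | 40-53 | 40-52 |
| 64 | 85 | 21 | 74.5 | 54-74 | 53-73 |
| 85 | 106 | 21 | 95.5 | 75-95 | 74-94 |
| 106 | 127 | 21 | 116.5 | 96-116 | 95-115 |
| 127 | 148 | 21 | 137.5 | 117-137 | 115-136 |

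The first six windows reproduce exactly. In the last five:

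- Every upper limit is one day short, as if the even-gap subtraction had been applied to an odd gap.
- The lower limits for Days 64, 85 and 106 are one day early.
- The lower limit for Day 127 is two days early (115 against 117).

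**Effect on assignment.** Day 115 is the only day in two windows. It is 115 − 106 = 9 days from one visit and 127 − 115 = 12 from the other. Days 53, 74, 95 and 116 go to the later visit, 11 days away, although the earlier visit is 10 days away (for Day 53: 53 − 43 = 10 and 64 − 53 = 11). Day 137 lies just past the listed range. If the next window starts there, it goes to Day 148 (11 days) rather than Day 127 (10 days).

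**Reading 2: count only the days strictly between visits.** Between Days 43 and 64 there are 20 such days, which is even, so the upper limit is 53.5 − 1 = 52.5, whole day 52. The same step gives 73, 94, 115 and 136, all as listed. Between Days 8 and 15, however, there are 6 days, also even, so the upper limit is 11.5 − 1 = 10.5, whole day 10, against the listed 11. All five windows followed by a 7-day gap (Days 8, 15, 22, 29 and 36) fail in the same way. With the ordinary midpoint, Day 2 fails as well (5 days between, odd, so 5 against the listed 4).

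**Why no single parity rule fits.** Gaps of 7 and 21 are both odd, and the counts strictly between (6 and 20) are both even, so any one parity rule treats them alike. The list does not: it adds 3 to the visit day for 7-day gaps (3.5 rounded down) and 9 for 21-day gaps (10.5 rounded down, less 1). There are five gaps of each kind, so at least five upper limits fail. Rounding up does no better: it gives 10 wrong upper limits under reading 1 and 6 under reading 2.

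**The case against.** The strongest objection is that the rule's wording admits reading 2, under which the five later upper limits are right and only the start of the Day 127 window (115 for 116) is wrong among those five. A reader might infer from the table that the documents prove those five windows wrong. They do not: they show that the rule and the list cannot both stand. Reading 1 is preferable because it reproduces the first six windows and gives every day to its nearest visit (Day 5, which is equidistant from Days 2 and 8, goes to Day 8). Reading 2 moves the failure to the 7-day windows without removing it.

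A second objection is that the list is generic. This partly stands. Chemistry and haematology have no Day 29 or Day 36 visit, and vital signs on those days are for Part A only (protocol Table 13). For chemistry, Day 43 follows Day 22, so the rule gives a midpoint of 32.5 and a Day 43 window starting at Day 33, not Day 40. But from Day 43 onward these assessments follow the 21-day spacing, so the conflict at the later boundaries remains.

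A third objection is that almost no data are touched, and this stands. Visits from Day 43 carry a 3-day allowance, so a visit within 3 days of its nominal day is assigned correctly. A Day 115 value could serve both visits only if the participant has no closer value in either window. A reader might infer that the safety results at large are distorted or that the windows overlap repeatedly. Neither is supported: one day overlaps, extremes and participant-level statistics use all values, and tumour-size visits have their own windows (SAP 4.2.7.2).

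**Conclusion.** The point holds as a minor correction. The Day 115 overlap is an error on any reading, and the documents do not resolve it. The list and the midpoint rule conflict on either reading of the even-number test.

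The effect is confined to late or unscheduled safety values on Days 53, 74, 95, 115, 116 and 137 in by-visit summaries. How many such values will arise cannot be known from the documents.

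Two assumptions matter. Naming Days 43 to 127 as the faulty windows rests on the gap-length reading. The Day 127 upper limit of 137 rests on Day 148 being the next visit; without it, Day 127 still fails on its lower limit.

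**What to change.** Replace the last five windows with 40-53, 54-74, 75-95, 96-116 and 117-137, and continue the pattern for later 3-weekly visits. This changes nine limits (five upper, four lower), follows the halfway rule, and leaves no gap or overlap. State that the even-number test refers to the difference between the two visit days, and that the same rule is applied to each assessment's own schedule, so that the list is not used where Days 29 and 36 are not scheduled.

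If the sponsor prefers the listed upper limits, it should start the Day 127 window at Day 116 and reword the rule to describe the list, including the different rounding after 7-day and 21-day gaps. That removes the overlap but still gives Days 53, 74, 95, 116 and 137 to the visit one day further away.

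Either way the cost is a few lines in the SAP and the matching window table in the programs. No data collection or study procedure changes.

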### **3.3.3 Handling of Unscheduled Visits**

See Section [3.3.2](#).

### **3.3.4 Multiplicity/Multiple Comparisons**

Not Applicable.

### **3.3.5 Handling of Protocol Deviations in Study Analysis**

The definitions of study specific Important Protocol Deviations (IPDs) are provided in the Protocol Deviation Assessment Plan (PDAP). IPDs identified as liable to influence statistical analysis may include, but are not limited to the following types of deviations:

- Participants who deviate from the core entry criteria as per CSP (e.g., Inclusion, exclusion, and discontinuation criteria), and participants who deviate from Substudy specific entry criteria as per CSP.
- Participants who received prohibited medications or therapies.
- Participants where the administration or dosing of IP is not per CSP.
- Procedure/ tests that are outside of required timeframes or not performed as specified in the CSP and are required for trial endpoints.

IPDs are tracked throughout the conduct of the study and reviewed by the study team with the frequency specified in the PDAP. Protocol deviations are evaluated on a case-by-case basis.

None of the deviations lead to the participant being excluded from any analysis sets described in the SAP, unless otherwise specified in the PDAP. If a deviation is serious enough to have a potential impact on the primary analysis, sensitivity analyses may be performed. The need for such a sensitivity analysis is decided during the data review meeting and before the Data-Base Lock (DBL). A list of all protocol deviations is reviewed and all decisions regarding how to handle these deviations are documented by the study team physician, clinical pharmacology scientist (CPS) and statistician prior to DBL and prior to the data cut-off for any primary analyses, in the Protocol Deviation Tool (PDT).

### **3.3.6 Missing Dates**

When partial dates exist in the data there are some general conventions for when the month or day are missing. These are described in the PhUSE guidance on partial dates, which are outlined here.

If the whole date is missing, it is more difficult to follow a general principle, and these are reviewed within the study and decided on how to be handled. General guidance for completely missing dates is provided below, but the guidance is assessed as necessary within the study.

Generally, the imputation of dates is used to decide if an observation is treatment emergent for adverse events (AEs) or concomitant medications. The imputed dates should not be used to calculate durations, where the results would be less accurate.

The following are the guidelines used when partial dates are detected in the study:

- For missing diagnostic dates (e.g., disease diagnosis) if day and/or month are missing use 01 and/or Jan. If year is missing, put the complete date to missing.
- For missing AE and concomitant medication start dates (with the exception of subsequent cancer therapy), the following is applied:
  - a. Missing day - impute the 1st of the month unless month is the same as month of the first dose of IP then impute first IP dose date.
  - b. Missing day and month - impute 1st January unless year is the same as first IP dose date then impute first IP dose date.
  - c. Completely missing - impute first IP dose date unless the end date suggests it could have started prior to this in which case impute the 1st of January of the same year as the end date.
  - d. Imputed start date should be no later than the end date.
- For missing AE and concomitant medication end dates, the following is applied:
  - a. Missing day - impute the last day of the month unless both the month and the year are the same as the last dose date or the primary analysis DCO date then impute the last dose date or the primary analysis DCO date.
  - b. Missing day and month - impute 31st December unless the year is the same as the last dose date or the primary analysis DCO date then impute the last dose date or the primary analysis DCO date.
  - c. Completely Missing – need to look at whether the AE/medication is still ongoing before imputing a date and when it started in relation to IP. If the ongoing flag is missing, then assume that AE is still present / medication is still being taken (i.e., do not impute a date). If the AE/medication has stopped and start date is prior to first dose date, then impute first dose date. Or if it started on or after first dose date then impute a date that is after the last dose of study drug date (e.g the day after).
- For missing subsequent therapy start dates, the following is applied:

- a. Missing day - impute the last day of the month unless both the month and the year are the same as the last dose date or the primary analysis DCO date then impute the last dose date +1 day or the primary analysis DCO date.
  - b. Missing day and month - impute 31st December unless the year is the same as the last dose date or the primary analysis DCO date then impute the last dose date + 1 day or the primary analysis DCO date.
  - c. Completely Missing – Impute last IP dose date + 1 day
  - d. Imputed start date should be no earlier than the last IP dose.
- Flags are retained in the database indicating where any programmatic imputation has been applied, and in such cases for AEs and concomitant medications, any durations would not be calculated.
  - If a participant is known to have died where only a partial death date is available, then the date of death is imputed according to the rules for imputing AE start dates unless this date is before the last date the patient is known to be alive from the database. In this scenario, the day after the last known alive date should be imputed. (See section [4.2.8.3](#) for further details).

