8.2.8 Survival Follow-up

All participants will be followed for survival until death, lost to follow-up, withdrawal of consent, or end of study whichever occurs first. Participants will be followed for survival by telephone calls, email, or clinic visits approximately every 12 weeks. During this period, information will be collected in the eCRF on survival status and any new anti-cancer therapies, and on any SAEs considered related to study intervention or study procedures.

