Thyroid function tests (TSH, free T4, free T3) ^d	X	X			8.2.5
Urinalysis	X	X			8.2.5
Coagulation parameters (PT/aPTT/INR/d-Dimer/Fibrinogen)	X	X			8.2.5
Pregnancy test (WOCBP) °	X	X	X		8.2.5
Virology (Hepatitis B and C) ^f		X			8.2.5
Biomarker Evaluations		1		. 	
CCI	Collect on progression				10.8.6.1.3

Study Period	ЕОТ	Follow-u	p Post EOT	LTFU	Details in	
Procedure/Study Day		Day 30 (± 7 days)	Day 90 (± 7 days)	Q12W Post Day 90 Visit	Section	
		Post EOT	Post Last Dose			
Serum for GDF15 target engagement	X	X	X		10.8.5.3.1	
Whole blood for CCI (refrigerated)	X	X	X		10.8.6.4	
Whole blood for flow cytometry	X	X	X		10.8.6.5	
CCI	X	X	X		10.8.6.3	
CCI	X	X	X		10.8.6.7	
CCI	X	X	X		10.8.6.7	
Plasma for circulating tumour DNA	X	X	X		10.8.6.6	
PK and Immunogenicity	 		•			
Parts A, B and C: AZD8853 PK			X		10.8.5.1 Table 18	
AZD8853 ADA	X	X	X		10.8.5.2 Table 19	
EOT and Follow-up Assessment	'	'	•			
Subsequent anti-cancer therapy	X	X	X	X	8.2.8	
Survival status (by telephone, email, or clinic visit)	X	X	X	X	8.2.8	

To include CT or MRI slices through T12 and L3.

Abbreviations: ADA = antidrug antibody; AE = adverse event; aPTT = activated partial thromboplastin time; CT = computerized tomography; DNA = deoxyribonucleic acid; ECG = electrocardiogram; ECOG = Eastern Cooperative Oncology Group; EOT = end of treatment; GDF15 = growth differentiation factor 15; INR = international normalised ratio; LTFU = long Term Follow-up; MRI = magnetic resonance imaging; NSCLC = non-small-cell lung cancer; CC | PK = pharmacokinetics; PT = prothrombin time; Q12W = every 12 weeks; RNA = ribonucleic acid; RECIST = Response Evaluation Criteria in Solid Tumours; SAE = serious adverse event; T3 = triiodothyronine; T4 = thyroxine; TSH = thyroid-stimulating hormone; WOCBP = woman of childbearing potential.

b If CT or MRI scan for disease assessment is performed ≤ 14 days prior to the EOT visit, it will not be required at EOT visit.

^c Will not be performed if previously confirmed disease progression has been documented.

d Free T4 and T3 measured if TSH is abnormal or if clinical suspicion of an AE related to the endocrine system.

^e A urine or serum pregnancy test is acceptable; if urine test is equivocal or positive then serum β-hCG testing should be performed for confirmation.

f Required for participants with a history of hepatitis B or hepatitis C.

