		

- Referenced additional information on DLT analysis set as added in the exposure section 4.2.1.1.

		Additional guidance provided on how to derive DLT analysis set

		

Section 3.3.2: Additional information has been added regarding visit windows and missing visit dates: “In the scenario that a complete visit date falls into the same visit as one that has been assigned due to missing data, the visit with the complete date is summarised”

		Added to further clarify how this data would be handled.
		

Section 3.3.5: Added that protocol deviations will be reviewed before the end of database lock and prior to the data cut-off for any primary analyses

		Protocol deviations need to also be reviewed prior to primary analyses (I.e. Substudy 1, Part A) where a data cut-off is used.

		

Section 3.3.6: Additional information has been added into the 'Missing dates' section. This provides more specific information about the date that should be imputed:

For the imputation of missing AE and concomitant medication end dates, where the date is completely missing, additional information has been added to the following text: "Or if it started on or after first dose date then impute a date that is after the last dose of study drug date". Added e.g., the day after."

Additional information added to clarify the imputation of data where a participant is known to have died: "If a participant is known to have died where only a partial death date is available, then the date of death is imputed according to the rules for imputing AE start dates unless this date is before the last date the patient is known to be alive from the database" - Added 'In this scenario, the day after the last known alive date should be imputed.'

Section 3.3.6: Additional information has been added into the 'Missing dates' section with reference to subsequent cancer therapy. This allows a more conservative approach to the imputation of subsequent therapy start date, which means more AEs will be treatment emergent:

"Missing day - impute the last day of the month unless both the month and the year are the same as the last dose date or the primary analysis DCO date then impute the

		Added to further clarify how this data would be handled.

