#### **4.2.3.3 Handling of dropouts and missing data**

Handling of missing TL data is described in Appendix A (Section [7.1](#)). Handling of missing subsequent treatment date is described in section [3.3.6](#).

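### A missing or partial start date for subsequent therapy can close the TEAE and on-treatment windows on the last-dose day, and the partial-date rules give no order when last dose and data cut-off both match (minor)

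*SAP*

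**What the plan says.** SAP 3.3.6 has four rules for subsequent-therapy start dates.

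- **Rule a (day missing):** use the last day of the month. If month and year match the last dose or the DCO, "then impute the last dose date +1 day or the primary analysis DCO date".
- **Rule b (day and month missing):** use 31 December, with the same pair of alternatives if the year matches.
- **Rule c:** "Completely Missing – Impute last IP dose date + 1 day".
- **Rule d:** nothing earlier than the last IP dose.

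Of wholly missing dates in general, 3.3.6 says that "these are reviewed within the study and decided on how to be handled", so rule c is a default.

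The date feeds two safety windows. In SAP 4.2.1.2 the treatment-emergent phase ends 97 days after the last dose, or on the day before subsequent therapy if that is earlier. SAP 3.3.1 sets the same 97-day limit and the same cut for visit-based safety data. SAP 4.2.3.3 uses the date for best overall response too: "Handling of missing subsequent treatment date is described in section" 3.3.6.

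The study also records when therapy had not yet started. Protocol 8.2.8 states that "information will be collected in the eCRF on survival status and any new anti-cancer therapies" during survival follow-up, and the row "Subsequent anti-cancer therapy" in Protocol Table 14 is marked at EOT, Day 30, Day 90 and every 12 weeks.

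**The concern.** Last dose + 1 day is one day above the floor in rule d, so it cuts the safety windows almost as early as the rules permit. Rules a and b otherwise choose a late date. A one-day shift in the last dose can therefore move the imputed start by weeks.

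The imputed date can also contradict the record. If the Day 30 contact recorded no new therapy and a later contact reports one without a date, last dose + 1 cannot be right.

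The two uses of the date pull in opposite directions. An early start is cautious for response, because fewer assessments count. For safety it is not cautious: AEs and SAEs that begin after the imputed start are only listed (SAP 4.2.1.2.1, Protocol 9.4.2). AE and SAE incidence is a primary endpoint, and SAEs are summarised in the same way as TEAEs.

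Separately, rules a and b offer two values and do not say which to use when last dose and DCO fall in the same month or year as the partial date. Two programmers could follow the text and get different TEAE tables.

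**Working it through.** **Inputs.** Window of 90 + 7 = 97 days after last dose (SAP 3.3.1 and 4.2.1.2), which reproduces the SAP's figure. Therapy start dates come from rules a to c. Contacts are at Day 30 ± 7 after EOT and Day 90 ± 7 after last dose (Protocol Table 14). The calendar dates below are illustrative assumptions.

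**Formula.** Days kept = max(0, min(97, start − last dose − 1)).

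**Rule c.** Start = last dose + 1 gives 1 − 1 = 0 of 97 days kept. The days lost depend on the true start:

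| True start (days after last dose) | Days that should be kept | Kept under rule c |
|---|---|---|
| 22 | 21 | 0 |
| 64 | 63 | 0 |
| 98 or later | 97 | 0 |

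Death, the DCO or withdrawal would shorten the true figure.

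**Against the contact record.** A contact D days after last dose that recorded no therapy means start ≥ D, so at least D − 1 days were therapy-free.

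- Day 30 contact (D = 23, 30, 37): 22, 29, 36 days dropped. This takes EOT to be on the last-dose day; a later EOT raises these figures.
- Day 90 contact (D = 83, 90, 97): 82, 89, 96 days dropped.

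**Rules a and b resolved to last dose + 1.**

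- Same month, widest case (last dose on the 1st, true start on the 31st): 31 − 1 − 1 = 29 days lost.
- Year only: up to 97 days lost. This needs a last dose on or before 24 September, since 24 September + 98 days = 31 December.
- Jump in rule a, with the DCO in a later month and therapy recorded as May 2023: last dose 30 April gives 31 May and 30 days kept; last dose 1 May gives 2 May and 0 kept.

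**Both dates match.**

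- Month: last dose 2 June 2023, DCO 30 June 2023, therapy June 2023. The start is 3 June (0 kept) or 30 June (27 kept). The widest case is 0 versus 29.
- Year: last dose 10 March 2023, DCO 30 June 2023, therapy 2023. The start is 11 March (0 kept) or 30 June (97 kept, because the window ends on 15 June).

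**Effect on a rate.** An affected participant changes the SAE rate only if an SAE falls in the lost days and none was already counted: 1/9 = 11.1 points in a cohort of 9, 1/40 = 2.5 points in an expansion of 40, otherwise 0.

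**The case against.** The strongest reply is that 3.3.6 already sends wholly missing dates to study review, and an undated therapy reported after a clean contact is what such a review should catch. A changed rate also needs a long chain: a recorded therapy, a missing or matching partial date, no correction, an event in the lost days, and none counted before. Sites ask about new therapy at every follow-up contact. Where only one date matches, the two values in rules a and b read naturally as respective. Using one derived date for all purposes is a legitimate simplification.

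Most of this stands as to size. It does not remove the point. The review clause gives no criterion for departing from rule c and does not reach the partial dates in rules a and b. It also leaves the double match unsettled.

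Three stronger readings are tempting, and the documents do not support them.

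- **That rule c defeats the SAP's own aim.** The Amendment History describes the approach as one "which means more AEs will be treatment emergent". The general start-date rule reads "Completely missing - impute first IP dose date unless the end date suggests it could have started prior"; applied to subsequent therapy it would give the first dose date. Rule c keeps the whole treatment period, so against that rule it does move in the stated direction. The AE start rule also concerns a different variable.
- **That 97 days of laboratory and ECG data are lost.** Protocol Table 14 schedules ECG at EOT only, and chemistry, haematology and coagulation at EOT and Day 30 only.
- **That the main analysis should not truncate at all when the date is unknown.** Protocol 9.4.2 limits TEAEs to those before subsequent therapy, and here a therapy is known to have started.

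**Conclusion.** The point holds at minor severity. When a subsequent therapy is dated at last dose + 1, both safety windows keep 0 of 97 post-dose days, even against a contact that recorded no therapy. The loss is at most 29 days for a same-month date and at most 97 for a year-only or wholly missing date. The double match leaves the result undefined: 0 versus up to 29 days by month, and 0 versus up to 97 by year.

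Where the true start was later, the error lowers AE and SAE rates. DLT tables and the all-participant death summary are not affected. The documents do not say how many participants would be affected; it is probably few. The truncation itself comes from the protocol and is not in question, only the imputed date. A reader might infer a material bias in the primary safety endpoint; the documents do not show one.

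**What to change.** For the TEAE and on-treatment windows only, amend SAP 3.3.6 before database lock:

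1. Impute no earlier than the last contact that recorded no new therapy.
2. In rules a and b, drop the last dose + 1 exception. Use the last day of the known month or 31 December, capped at the earliest of any recorded stop date of that therapy, death and the DCO. State that the DCO is a cap and not an alternative value. In the examples above this gives 29 days kept for May 2023 with last dose 1 May, 27 for June 2023, and 97 for the year-only date.
3. For a wholly missing date, use the contact-bounded date in place of last dose + 1. Use the imputation flag that the SAP already retains to show separately the AEs whose treatment-emergent status depends on an imputed date. Add a sensitivity display with no truncation before last dose + 97 days.

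Leave the date used for BOR, ORR and DCR under the current rules.

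The cost is a few lines of SAP text and a second derived date for the same therapy. The downside is that a few AEs that began after the new therapy may be counted as treatment-emergent; the flagged display makes them visible.
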